3.4 General Analysis Considerations

3.4.1 **Deriving Study Day**

The following definitions are used for study day:

- Day 1 = Date of first dose of AC699 received
- Study Day = Study date Date of first dose of AC699 received + 1 if study date is on or after date of Date of first dose of AC699 or Study Day = Study date Date of first dose of AC699 received if study date is before date of Date of first dose of AC699.

3.4.2 **Baseline Definition**

Baseline value is defined as the last non-missing value prior to the first dose of *AC699*. For assessments without time collected such as physical examination, vital signs, labs, and Eastern Cooperative Oncology Group (ECOG), those that occur on Study Day 1 are considered as pre-dose.

3.4.3 Missing Data

3.4.3.1 Handling of Partial Dates

All start and end dates, when applicable, for safety, efficacy, and exposure to study treatment must be complete dates (i.e., day, month and year must be present). Dates associated with prior medications, prior therapies, and other historical data, whether complete or not, that typically are not involved in direct calculations affecting safety or efficacy will be listed as recorded on the case report form (CRF).

When defining TEAEs, if a partial date is adequate to determine when the onset date of an event occurred relative to first dose of study treatment, then the partial date will be used. If a partial date does not provide enough information to determine the onset date relative to first dosing date, then the adverse event (AE) will be assumed as treatment emergent. AEs will be assumed to be treatment-emergent, unless there is clear evidence (through comparison of partial dates) to suggest that the AE started prior to the first dose of study treatment.

The following rules provide an algorithm to impute a complete AE start date when determining if an AE is treatment-emergent in the scenario where the start date is missing or partially missing.

- AE start date is missing day and month:
 - o If the year is the same as the year of the treatment start date, the day and month of the treatment start date will be assigned to the missing fields.

- o If the year is prior to the year of the treatment start date, December 31 will be assigned to the missing fields.
- o If the year is after the year of the treatment start date, January 1 will be assigned to the missing fields.
- AE start date is missing day only:
 - o If the month and year are the same as the month and year of the treatment start date, the day of the treatment start date will be assigned to the missing day.
 - o If the year is before the year of the treatment start date, or if both years are the same but the month is before the month of the treatment start date, the last day of the month will be assigned to the missing day.
 - o If the year is after the year of the treatment start date, or if both years are the same but the month is after the month of the treatment start date, the first day of the month will be assigned to the missing day.
- AE start date is completely missing:
 - o If the AE end date is complete and after the treatment start date, the treatment start date will be assigned to the missing AE start date.
 - o If the AE end date is complete and before the treatment start date, the AE end date will be assigned to the missing AE start date.
 - Otherwise, the AE start date will be assigned to the treatment start date.

[Note: If the AE end date is complete and the imputed AE start date is after the AE end date per the above rules, the AE start date will be imputed as the AE end date.]

Similarly, the same principles as TEAE apply when defining whether a medication is concomitant.

For durations using historical data, the following rules apply:

• Missing months will be imputed as July and missing days will be imputed as the 15th.

[Note: If the above rule results in a negative duration and only the day is missing, the day will be imputed as the first of the month. If the month is missing, the month will be imputed as the month of first dose of study treatment, and day will be imputed as the first of the month.]

3.4.4 Analysis Visit Windows

No visit windowing will be performed in the analyses. Assessments will be summarized under the visit as entered in the database.

3.4.5 **Descriptive Statistics**

Summaries will be presented by each dose level and overall unless stated otherwise.

Qualitative variables, such as binary, ordinal, and categorical variables, will be presented as frequencies and percentages. Percentages will be rounded to one decimal place.

Continuous variables will be presented with the number of non-missing values, mean, standard deviation, median, minimum, and maximum values. Minimum and maximum will be displayed with the same accuracy as the original data; mean and median will be rounded to one additional decimal place compared to the original data; standard deviation will be rounded to two additional decimal places compared to the original data.

If data are available for less than three participants, no summary statistics other than number of non-missing values, minimum, and maximum will be presented. The remaining summary statistics will be presented as "NC" (Not Calculable).

3.4.6 Graphical Presentation

Data may be presented graphically where appropriate.

3.4.7 Analysis Software

Analyses will be performed using SAS® version 9.4 or higher.

3.5 Analysis of Efficacy Variables

3.5.1 Time-to-Event Variables

The proportion of events and censored observations will be summarized with frequency and percentage. Medians of DoR and PFS along with the 95% CIs will be calculated from the Kaplan-Meier (KM) analysis. Q1 and Q3 will also be displayed.

The CIs will be calculated using the Brookmeyer and Crowley method after applying the log-log transformation (Kalbfleisch et al, 1980).

KM curves will be produced to provide a visual description of the differences between the dose levels.

Sample SAS code is provided in Appendix A: Sample SAS Code.

3.5.2 Analysis of Response Rate

The ORR, CBR, and DCR will be summarized with frequency and percentage with a 95% CI by Clopper-Pearson.

Sample SAS code is provided in Appendix A: Sample SAS Code.

4 Trial Population

4.1 **Participant Disposition**

Participant disposition will be summarized by frequency and percentage for all participants.

The following categories will be tabulated:

- Participants screened
- Participants assigned to AC699
- Participants who received AC699

- o Participants with ongoing AC699 treatment at data cut-off
- Participants who discontinued AC699, and reasons for discontinuation (from CRF)
- Participants ongoing study at data cut-off
 - Participants who discontinued study, and reasons for discontinuation (from CRF)
- Participant inclusion to analysis sets: Full, Safety, and Efficacy.

Participants in each analysis set will be summarized by frequency for all participants.

Participant disposition data will be listed, inclusive of treatment discontinuation, study discontinuation, eligibility, and analysis set inclusion.

4.2 Baseline Participant Characteristics

Participants with missing categorical data will be tabulated as a missing category and will be included in the denominator for percentages overall.

Baseline participant characteristics will be listed, inclusive of demography, clinical characteristics, medical history, and disease characteristics. Tables will be presented as applicable.

4.2.1 **Demographic Characteristics**

The following demographic characteristics will be summarized:

- Age (years) at Informed Consent, calculated as the difference in years between the Date of Informed Consent and the Year of Birth, summarized continuously and categorically: 18 − <50, ≥50 <65, ≥65
- Sex (Female, Male)
- Race (American Indian or Alaskan Native, Asian, Black or African American, Native Hawaiian or Other Pacific Islander, White, Other, Not Reported, Unknown)
- Ethnicity (Hispanic or Latino, Not Hispanic or Latino, Not Reported, Unknown)

4.2.2 Clinical Characteristics

The following baseline clinical characteristics will be summarized:

- ECOG performance status
- ECOG performance status at post-baseline assessments
- ECHO screening outcome
- Tumor (radiographic) assessments
- Laboratory test (HIV, HBV, and HCV) outcome
- Vital signs including weight and height

4.2.3 **Medical History**

Ongoing medical history will be summarized by system organ class (SOC) and preferred term (PT) using Medical Dictionary for Regulatory Activities (MedDRA) version 25.0 or higher.

4.2.4 Disease Characteristics

The following baseline participant disease characteristics will be summarized:

- Time from initial diagnosis of disease to enrollment (months), calculated as (*Date of First Dose of AC699 Date of Initial Diagnosis* + 1) / 30.4375 (refer to section 3.4.3.1 for date imputation rules if date of initial diagnosis is partial)
- ESR1 mutation status

4.3 **Prior Anticancer Therapy**

Prior anticancer therapies (including systemic therapy, radiation, and procedures) will be summarized separately by frequency and percentage of participants who received each.

Systemic therapies will be coded and subcategorized by class using the World Health Organization (WHO) Drug Dictionary Global September 2021 or higher. Radiation and surgeries will be coded using MedDRA version 25.0 or higher.

All prior anticancer therapies will be listed.

4.4 Prior and Concomitant Medications

All medications will be coded using the WHO Drug Dictionary Global September 2021 or higher. Prior medications are those taken before the start of study treatment. Concomitant medications are those taken after the start of study treatment, including those that started prior to study treatment but were taken on/after start of study treatment. A given medication may be both prior and concomitant. Transfusions can be prior or concomitant medication but will not be considered as a procedure.

The frequency and percentage of participants who received concomitant medications will be summarized by Anatomical Therapeutic Chemical Classification and preferred name.

All prior and concomitant medications will be listed.

4.5 Concomitant Procedures

All concomitant procedures will be listed and coded using MedDRA version 25.0 or higher.

4.6 Subsequent Anticancer Therapy

Anticancer therapy initiated after patient's discontinuation from the study treatment will be summarized by frequency and percentage of participants.

- Participants who received subsequent systemic therapy(ies)
- Participants who received subsequent procedure(s)
- Participants who received subsequent radiation

All subsequent anticancer therapies will be listed.

5 Efficacy Analysis

All efficacy data will be presented in listings. Tables and figures will be presented as applicable. All efficacy analyses will be performed using the EFF as a whole and subdivided by ESR1 mutational status.

The secondary endpoints are ORR, CBR, DoR, DCR, PFS.

The exploratory endpoints are as follows:

- 1. Change of $ER\alpha$ expression in tumors from baseline to post-treatment in paired biopsies.
- 2. Correlation between circulating tumor cell count at baseline and post-treatment and anti-tumor activity (ORR, CBR, DOR, DCR, and PFS)
- 3. Correlation between estrogen receptor gene 1 mutational status and anti-tumor activity (ORR, CBR, DOR, DCR, PFS).
- 4. Correlation between circulating tumor DNA levels at baseline and post-treatment and anti-tumor activity (ORR, CBR, DOR, DCR, PFS).

5.1 **Endpoint Foundations**

5.1.1 **Objective Tumor Response**

Tumor response will be evaluated using RECIST 1.1 criteria (Eisenhauer, et al 2009), every 8 weeks (\pm 5 days) for the first year of treatment, and then once every 16 weeks (\pm 5 days) thereafter or until disease progression (as determined by the investigator).

The response categories are as follows:

- Complete response (CR)
- Partial response (PR)
- Stable disease (SD)
- Progressive disease (PD)

Not Evaluable (NE)

The overall response to each assessment will be determined by the Investigator.

5.1.2 Time-to-Event Variables

Time-to-event variables are defined as:

Time-to-Event (months) = (End Date - Start Date + 1) / 30.4375

 $DOR = (Earliest\ Date\ of\ Progression\ or\ Death-Date\ of\ First\ Documented\ CR\ of\ PR + 1)/30.4375.$

Start Dates

For all time to event variables other than DoR, the date of first dose of AC699 will be used as the start date.

The start date for DoR will be the date of first PR or CR, which has been subsequently confirmed.

End Dates

For DoR and PFS, the following rules will be used to derive the end dates for these endpoints:

- Events always take precedence to Censoring
- If multiple event dates are applicable, the earliest date will be used.
- If multiple censoring dates are applicable, the latest date will be used.

Table 2 shows data sources that can be used to determine end dates.

Table 2: Data Sources for End Dates

Date	Data Source	
Date of Death	Death CRF	
Date of Progression	Using RECIST 1.1 criteria, the earliest of the dates from the components that triggered the overall PD response from the Target Lesions, Non-target Lesions and New Lesions CRFs.	
Date of Last Evaluable Tumor Assessment	The latest data from the Target Lesions, Non-Target Lesions, and New Lesions CRFs reflecting the overall response, where the overall response is evaluable (i.e., not missing or NE), prior to further subsequent anticancer therapy if initiated.	
Date of Subsequent Anticancer Therapy	The earliest date is from the Subsequent Systemic Therapy, Subsequent Radiation, and Subsequent procedure CRFs.	

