5.2 End of Study Treatment (EOT)

Patients will be discontinued from study treatment for any of the following reasons:

- Objective disease progression (Patients who are receiving clinical benefit in the opinion of the treating Investigator may be allowed to stay on study treatment after consultation with the Medical Monitor and Sponsor Representative)
- Intolerable toxicity that are irreversible thought to be related to study drug
- Treatment discontinuation criteria as per Dose Modification criteria (See Section 6)
- Conditions requiring therapeutic intervention not permitted by the protocol
- Intercurrent illness interfering with the patient's ability to follow study requirements (treatment or assessments); this will be at the Investigator's discretion

CONFIDENTIAL

Study Drug: AC699 Sponsor/Development Innovations Study Numbers: AC699-001/BRE 401

- Another condition leading to patient's inability to comply with study requirements
- Patient lost to follow-up
- Patient withdraws consent from study treatment or study participation altogether
- Start of a new anti-cancer therapy
- Patient's death
- Patient's participation in the study is terminated by Investigator
- Study termination

After discontinuation from protocol treatment, patients must be followed for AEs for 30 days after their last dose of study drug. Patients discontinuing study treatment prior to disease progression (per RECIST v1.1) will go on to extended follow-up. During extended follow-up response assessments will be performed as described in Section 7.4.3. All new AEs occurring during the 30-days following termination of treatment must be reported and followed until resolution or stabilization unless, in the opinion of the Investigator, these values are not likely to improve because of the underlying disease. In this case, the Investigator must record his or her reasoning for this decision in the patient's medical records and indicate that the outcome is not resolved on the AE pages of the electronic case report form (eCRF).

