5.2.4 Progression-Free Survival

PFS (months) is the time from date of first dose of AC699 to the first documentation of disease progression or death due to any cause. Participants who have neither progressed nor died will be censored.

Refer to Table 4 for the event/censoring rules and dates to be used.

Table 4: Progression Situations and Event/Censoring Rules

Situation	Date of Event or Censoring	Outcome
No baseline assessment	Date of first dose of AC699	Censored

Situation	Date of Event or Censoring	Outcome
Progression documented between scheduled visits, or after one missed or non-evaluable assessment	Date of progression (see Table 2)	Event
No progression	Date of last evaluable tumor assessment (see Table 2)	Censored
Treatment discontinuation for undocumented progression (e.g., clinical progression based on investigator claim)	Date of last evaluable tumor assessment (see Table 2)	Censored
Treatment discontinuation for adverse event or other reason	Date of last evaluable tumor assessment (see Table 2)	Censored
Further anticancer therapy started	Date of last evaluable tumor assessment (see Table 2)	Censored
Death before first PD assessment	Date of last evaluable tumor assessment (see Table 2)	Event (PFS)
Death before the next scheduled tumor assessment, or after one missed tumor assessment	Date of death (see Table 2)	Event (PFS)
Death, or progression after two or more missed tumor assessments	Date of last evaluable tumor assessment (see Table 2)	Censored

The rule to determine whether there are at least two missing tumor assessments is based on the interval between the last evaluable tumor assessment date and the event date. If the interval is greater than twice the protocol-specified interval between the tumor assessment plus the protocol-allowed time window around the assessment, then the number of missing assessments is two or more.

For the first 52 weeks, tumor assessments are to be performed every 8 weeks (\pm 5 days); therefore, the threshold will be 18 weeks. After the first 52 weeks, tumor assessments are to be performed every 16 weeks (\pm 5 days); therefore, the threshold will be 34 weeks.

6 Safety Analysis

All safety data will be presented in listings. Tables and figures will be presented as applicable.

Exposure to Study Treatments

Exposure to AC699 will be summarized in the following ways:

- Total Treatment Duration (days), calculated as *Date of Last AC699 Dose Date of First AC699 Dose + 1*.

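### As worded, SAP Table 2 lets the progression scan count as the last evaluable assessment, so Table 4's two-missed-scan rule never censors a progression

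*SAP*

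**What the plan says.** SAP 5.1.2, Table 2, defines the date of last evaluable tumor assessment as the latest lesion-form date "where the overall response is evaluable (i.e., not missing or NE), prior to further subsequent anticancer therapy if initiated". Those are its only two limits. SAP 5.1.1 lists PD and NE as separate response categories. Table 2 takes the progression date as "the earliest of the dates from the components that triggered the overall PD response".

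SAP 5.2.4, Table 4, governs both PFS and DoR. Its last row, "Death, or progression after two or more missed tumor assessments", is censored at the date of last evaluable tumor assessment, with a cross-reference to Table 2. The note under the table decides whether two scans were missed "based on the interval between the last evaluable tumor assessment date and the event date". The thresholds are 18 weeks while scans are every 8 weeks and 34 weeks once they are every 16 weeks.

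Three other provisions bear on this:
- SAP 5.1.2 gives events precedence over censoring, without exception, and takes the earliest date when several event dates apply.
- Protocol 5.2 says that patients with objective progression who are still benefiting "may be allowed to stay on study treatment after consultation with the Medical Monitor and Sponsor Representative".
- Protocol 10.4.2 defines PFS without any missed-scan rule, so the SAP is the only source for this one.

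**The concern.** The last row of Table 4 is there so that a long stretch without scans is not counted as observed progression-free time. It needs an anchor before the gap. Table 2 supplies an anchor that, for any patient with progression, is the PD scan itself, or a later scan if the patient was treated beyond progression. The same date does two jobs in the row, as the start of the gap and as the censoring date, so one loose definition undermines both.

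What is at stake is whether two programmers working from the same text would derive the same PFS and DoR. One who follows the cross-reference gets an event on the PD date. One who follows the evident purpose of the row censors before the gap. Medians and Kaplan-Meier curves are presented by dose level, and efficacy is also split by ESR1 status. Expanded dose levels hold about 15 patients in the SAP (20 in the protocol), and DoR uses responders only. In groups of that size one or two reclassified patients could move a median.

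**Working it through.** **Step 1: reproduce the thresholds.** The inputs are scan intervals of 8 and 16 weeks (56 and 112 days) and a window of 5 days, all from SAP 5.2.4.
- Twice the interval plus one window: (112 + 5)/7 = 16.7 weeks and (224 + 5)/7 = 32.7 weeks. This does not give 18 and 34.
- Twice the sum of interval and window: 2 × (56 + 5) = 122 days = 17.4 weeks, and 2 × (112 + 5) = 234 days = 33.4 weeks. Rounded up, these are 18 and 34.
- With the window taken as one week, as SAP 5.2.1 does for stable disease: 2 × (8 + 1) = 18 and 2 × (16 + 1) = 34 exactly.

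The plan's figures are therefore reproduced as twice (interval plus window).

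**Step 2: which scan is the anchor?** PD is not missing and not NE. If no new therapy has begun, the PD scan meets both limits in Table 2 and is the latest scan. The progression date is the earliest component date of that assessment, while the anchor is the latest form date. Event date minus anchor is therefore zero, or slightly negative if the components were imaged on different days. A later evaluable scan on treatment beyond progression makes it more negative.

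**Step 3: compare the two anchors on assumed timelines.** Months = (end date − start date + 1)/30.4375, from SAP 5.1.2. A scan at week w falls on study day 1 + 7w.

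| | 8-week scans | 16-week scans |
|---|---|---|
| Last scan before the gap | week 16 (day 113) | week 64 (day 449) |
| Scans missed | weeks 24, 32 | weeks 80, 96 |
| PD | week 40 (day 281) | week 112 (day 785) |
| Gap from scan before the event | 24 weeks > 18 | 48 weeks > 34 |
| Result with that anchor | censored, 113/30.4375 = 3.71 months | censored, 449/30.4375 = 14.75 months |
| Gap with Table 2 as worded | 0 weeks | 0 weeks |
| Result as worded | event, 281/30.4375 = 9.23 months | event, 785/30.4375 = 25.79 months |
| Difference | 168 days, 5.52 months | 336 days, 11.04 months |

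As a control, take a last scan at week 8, week 16 missed and PD at week 24. The gap from the earlier scan is 16 weeks, below 18, so PD is an event under either anchor. With the pre-event anchor the rule separates one missed scan from two, as intended. With Table 2 as worded it never fires for progression.

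**Step 4: direction of the effect on the median.** Take the 8-week patient above plus three others, all hypothetical.
- Others progress at weeks 48, 56 and 64. If the index patient is censored at week 16, S(48) = 2/3 and S(56) = 1/3, so the median is 56 weeks. With an event at week 40, S(40) = 3/4, S(48) = 1/2 and S(56) = 1/4, so the median is 48 weeks (52 by the midpoint convention). The median falls.
- Others progress at weeks 24, 32 and 48. If the index patient is censored at week 16, S(24) = 2/3 and S(32) = 1/3, so the median is 32 weeks. With an event at week 40, S(24) = 3/4, S(32) = 1/2 and S(40) = 1/4, so the median is 32 weeks (36 by the midpoint convention). It stays the same or rises.

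The sign depends on the other patients.

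**The case against.** The strongest reply is that the intent is plain. Table 2 only lists data sources. The operative rule is the note under Table 4, and comparing a gap with 18 or 34 weeks makes sense for progression only if the anchor precedes the event. A careful programmer would read it so. That stands as evidence of intent, and it means this is a defect of wording and not proof that the analysis will be run wrongly. It does not remove the problem, because Table 4 explicitly refers back to Table 2 for the date and the precedence sentence in SAP 5.1.2 pushes toward counting the event.

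It is also fair to say that an event on the documented PD date agrees with the protocol's PFS definition. That is an argument for deciding whether the row is wanted. It does not support leaving in place a row that cannot operate for progression.

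Two stronger readings are tempting. One is that the patient is censored on the PD date, which would credit the whole gap and also remove the event. The text does not lead there. The note gives the counting rule, a zero gap means the row does not apply, and so no censoring date is taken from it. That outcome would require counting missed scans some other way, such as by visit, and then using Table 2 for the date. The other is that PFS and DoR are biased upward. As worded, the rule adds an event as well as follow-up time, and Step 4 shows the median can fall.

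Treatment beyond progression adds little: it can move the anchor later, but the earliest event date still governs.

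**Conclusion.** The point holds as an internal contradiction in the SAP. Applied literally, Table 2 disables the progression half of Table 4's last row, and a progression after two or more missed scans is counted as an event on the PD date.

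In the assumed timelines the affected patient's end date moves by 5.5 months (8-week scans) or 11.0 months (16-week scans), and the status changes from censored to event. These sizes rest on exactly two consecutive missed scans at nominal times. The documents give no rate of missed scans, so neither the number of affected patients nor the shift in any median can be derived.

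The scope is limited. For a death without prior PD, the last evaluable scan precedes death and the interval is measured correctly. The row for no progression is also sound, because no PD scan exists. PFS and DoR are secondary and descriptive, there is no hypothesis test, and the primary safety endpoint is untouched. It should still be corrected before the analysis datasets are programmed.

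**What to change.** In the last row of Table 4 and in its note (or once, in Table 2), define the anchor as *the last evaluable tumor assessment before the first documented progression or death*. State that this one date is both the start of the gap and the censoring date.

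In SAP 5.1.2, state that this row is an exception to the rule that events take precedence over censoring. Without that sentence a reader could still keep the week-40 progression as an event after the anchor is corrected.

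The cost is a few phrases in the SAP, with no new data, visits or protocol amendment.
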